3.3.2 Secondary Endpoint

Progression-free survival.

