6.0 SUBJECT ELIGIBILITY

6.1 Inclusion Criteria

- Adult, non-pregnant patients with biopsy-proven or clinically obvious primary, recurrent or metastatic breast cancer
- Breast cancer from ER+ primary that is seen on other imaging tests. Tumor ER expression must have been confirmed by immunohistochemistry of primary tumor or recurrent disease.
- At least one site of disease 1.5 cm or greater is needed to meet the spatial resolution limits of PET imaging.
- Patients must have been off tamoxifen or other estrogen receptor blocking agents for at least 6 weeks and off chemotherapy for 3 weeks for the initial baseline FES.
- Patients must be selected for an endocrine targeted therapy regimen for treatment of their breast cancer by the referring oncologist. Selected treatments may be part of experimental treatment protocols for which the patient would be separately consented.
- Patients must be willing to undergo serial imaging procedures.
- Patients must agree to allow access to clinical records regarding response to treatment and long term follow up.
- Ability to understand and the willingness to sign a written informed consent document.

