Repeat FES PET scan and FDG PET scan: Patients will undergo a second FES PET and FDG PET scan after starting endocrine targeted therapy to assess the effect of therapy on ER expression and estradiol binding to the receptor. Exact timing of the second FES and FDG scans, will depend upon the endocrine targeted regimen and dosing, but typically will be 1 – 12 weeks after starting therapy.

The repeat FDG PET may be omitted in patients on SERD therapies, where repeat FES PET is used primarily to evaluate residual ER availability rather than tumor response. This will be determined by requirements of the co-enrolling companion therapeutic protocol.

Optional Biopsy: In patients who consent to optional biopsies, an early response tumor sample will be obtained 1-12 weeks after starting the selected therapy. This biopsy should take place after completion of the repeat PET imaging and should target the same tumor site as the baseline biopsy. A whole blood sample may be drawn for correlation of steroid hormone levels in serum and biopsy tissue.

Week 1 to 20 years after [18F]FES PET Scan: Clinical follow-up will continue for up to 20 years, time of progression and date of death will be recorded. For some patients, especially those receiving two endocrine-directed treatments, a third FES PET scan and additional research FDG PET scan may also be obtained 1-12 weeks after the second FES PET scan. For each patient, a maximum of 3 FES PET and 3 FDG PET scans would be done.

A study calendar is included in Appendix A.

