FES static survey images will undergo region of interest (ROI) analysis as follows: Lesion location will be identified using FES scans along with FDG scans with reference to CT or ultrasound. All patients will have undergone clinically motivated FDG PET scans for staging prior to FES imaging. CT, MRI, ultrasound or bone scan will be available on all patients with suspected metastatic disease. Although FES and FDG imaging will be performed on separate days, studies will be performed with the patient in the same position and images will be co-registered using common anatomic landmarks such as the lung outline, cardiac blood pool, liver contour, and body outline. In this way, regions can be drawn on the FDG images and transferred to the FES images for quantitative analysis which is important in identifying tumor locations, especially in ER-negative tumors which are not visualized on FES imaging. For each disease site, a set of 1.5 cm diameter regions on three adjacent planes with the highest lesion FES uptake will be drawn to determine maximal FES uptake. Up to the 10 largest sites seen on the static torso survey will be quantified. Partial-volume correction will not be used because only sites 1.5 cm or greater diameter will be included in quantitative analysis.

FES uptake will be quantified using the standard uptake value (SUV, defined below). For each site, we will record the average and maximum SUV within the ROI set for each site of disease.

For each subject, we will calculate the average and range of FES uptake values for active disease sites. The FES uptake will be compared with subsequent response to endocrine therapy and TTP.

FDG studies will also be quantified for uptake in a similar fashion. On FDG studies, simple SUVs will be generated using the average tissue activity over the imaging period, which are typically 45 and 75 minutes after injection. We will record the maximum FDG SUV for each site of disease. Uptake at tumor sites using the standardized uptake value (SUV) is calculated as:

$$SUV = \frac{\overline{C}_t}{ID / wt}$$

where \overline{C}_t is the average tumor uptake after injection for the period of the static imaging for torso surveys (MBq/mL), ID is the injected dose (GBq) and wt is the patient's weight (kg). Note that either standard or metric units can be used to calculate SUV as long as only one type of unit is used for each calculation.

Biologic Correlates

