Measurement of these tumor-associated indices may enhance the predictive value of PET FES, provide information to better understand mechanisms of resistance to endocrine therapy, and eventually determine which patients are likely to appreciate clinical benefit as a result of endocrine therapy, even in the absence of an objective response.

Time to progression (Progression-free survival): Time to progression (and progression-free survival) will be measured as the time from the start of endocrine therapy to the time the patient is first recorded as having disease progression. If a patient never progresses while being followed, the patient will be censored at the time he/she terminates follow-up or by date of disease progression or death.

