17.0 STATISTICAL CONSIDERATIONS

Analysis Plan

The primary application will be pilot studies with enrollment of about 20 patients, in which the in vivo effects of endocrine-targeted therapy are measured by serial FES PET. The primary endpoints will be quantitative and qualitative measures of FES uptake, and measures of change in FES uptake between pre-therapy and post-therapy scans (Section 6.10.2). Additionally, patients will be followed for disease progression. Associations among FES and FDG PET measures, progression, and biological correlates (Section 6.10.3) may be examined in descriptive analyses.

An expected primary analysis is to examine whether FES uptake changed on average between serial assessments. This may be assessed by a one-sample test of the percent change in FES SUV. For example, a one-sided test at the 0.05 level of significance could evaluate whether the average percent change in FES SUV was greater than 20%, considered a biologically significant change. In serial FES SUV measurements of heavily-pretreated breast cancer patients, change in FES SUV was approximately normally distributed with a standard deviation of about 25 percentage points, for both patients treated with blocking therapy (tamoxifen or fulvestrant) or non-blocking therapy (aromatase inhibitor). Using this standard deviation and n=20 to test whether the average change was greater than 20%, the power would be 0.97 if the true change is 40%, and 0.85 if the true change is 35%. To conclude only that the average percentage change was different from zero (using a two-sided test at the 0.05 level of significance), power would be 0.95 to detect a true average change of 20% (and 0.85 if the true standard deviation were 30 percentage points).

Other analyses for pilot studies could examine what proportion of patients experienced a threshold in percentage change, or surpassed a targeted follow-up FES SUV value. These percentages will be reported using a 90% Wilson score binomial confidence interval. Width of these confidence intervals for pilot studies of n=20, n=25, and n=30 are given in Table 6.3 for a range of observed percentages.

Table 17.1: 90% Wilson score binomial confidence intervals (CIs) by percent observed and sample size.

observed percentage (CI) for n=20	observed percentage (CI) for n=25	observed percentage (CI) for n=30
0.1 (0.03, 0.26)	0.12 (0.05, 0.27)	0.1 (0.04, 0.23)
0.2 (0.09, 0.38)	0.20 (0.10, 0.36)	0.2 (0.11, 0.34)

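### Section 14.0 defines PFS and TTP by one rule that censors deaths, so the secondary endpoint named PFS is, as written, TTP.

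*Combined protocol and SAP*

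**What the plan says.** Section 3.3.2 lists a single secondary endpoint, "Progression-free survival", and does not define it there.

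The definition is in the last paragraph of Section 14.0, which handles two endpoints together: "Time to progression (and progression-free survival) will be measured as the time from the start of endocrine therapy to the time" of first recorded progression. The next sentence gives the censoring rule. It opens with the condition "If a patient never progresses while being followed" and continues: "the patient will be censored at the time he/she terminates follow-up or by date of disease progression or death".

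Elsewhere in Section 14.0, under Quantitative Assessment, the outcome is called TTP: "The FES uptake will be compared with subsequent response to endocrine therapy and TTP".

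Section 17.0 adds no definition. It says that patients will be followed for progression and that associations of the PET measures with progression "may be examined in descriptive analyses". Section 3.4 sets accrual at up to 20 patients.

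On data collection, Section 8.1 states: "Clinical follow-up will continue for up to 20 years, time of progression and date of death will be recorded".

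**The concern.** PFS counts the earlier of progression and death. TTP counts progression only and commonly censors deaths. Section 14.0 applies the second rule to both names. An analyst who follows it will report TTP as PFS, and a patient who dies without recorded progression will contribute a censored time where PFS requires an event.

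The design makes such deaths plausible, although the documents give no rate:

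- Follow-up runs for up to 20 years.
- Section 14.0 says the study itself does not evaluate response and may only record it when a treatment study collects it.
- Appendix A schedules no disease assessment during follow-up.
- Section 11.0 keeps every subject in survival follow-up, so deaths may be captured more completely than progressions.

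Sections 2.1 and 3.3 say that promising data will be used to design a multi-center phase II trial. A mislabelled time-to-event result could be carried into that planning.

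**Working it through.** **Text check.** The plan gives no median, event count, hazard ratio or power for PFS or TTP, so there is no figure to reproduce. The question is what the wording makes an event.

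| Item | Section 14.0 as written | What PFS requires |
|---|---|---|
| Start | Start of endocrine therapy | A stated origin; this one serves |
| Event | First recorded progression | First of progression or death |
| Death without progression | Censored at death | Event at death |
| Date of progression | Listed as a censoring date for patients who never progress | Event date |

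The last row is a contradiction within one sentence: a patient who meets its condition has no progression date. Sections 3.3.2, 8.1 and 17.0 do not repair either row, and none of them makes death a PFS event.

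**Direction.** At each death without recorded progression, the Kaplan-Meier estimate of PFS is multiplied by (1 − 1/number at risk). If the death is censored, the factor is 1. The curve with deaths censored therefore lies on or above the PFS curve at every time.

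**Size (illustration; s and the 12-month median are assumptions).** Let λp and λd be constant hazards of progression and of death without recorded progression, and let s = λd/(λp + λd), the share of first events that are such deaths.

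- PFS median = ln 2/(λp + λd)
- Median with deaths censored = ln 2/λp
- Ratio = (λp + λd)/λp = 1/(1 − s)
- When true PFS is 0.5, the deaths-censored curve reads 0.5^(1 − s)

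With k deaths among 20 first events, s = k/20 and the ratio is 20/(20 − k):

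| k | s | Ratio | Assumed 12-month median reads | Curve when true PFS is 0.5 |
|---|---|---|---|---|
| 0 | 0% | 1.000 | 12.0 | 0.500 |
| 1 | 5% | 1.053 | 12.6 | 0.518 |
| 2 | 10% | 1.111 | 13.3 | 0.536 |
| 4 | 20% | 1.250 | 15.0 | 0.574 |
| 6 | 30% | 1.429 | 17.1 | 0.616 |

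A simulation of 100,000 exponential times with deaths censored gave medians of 12.0, 12.7, 13.3, 15.1 and 17.1 months for the five rows. In 4,000 simulated samples of 20 at each s, the deaths-censored median was never below the PFS median of the same sample.

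**Sensitivity.** With a common Weibull shape c, the ratio becomes (1/(1 − s))^(1/c). At s = 20%, shape 0.8 gives 1.25^1.25 = 1.32 (32% inflation) and shape 1.5 gives 1.25^0.667 = 1.16 (16%).

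**Scale.** With 20 events, the 95% interval around a 12-month exponential median is 12 × exp(±1.96/√20) = 12 × exp(±0.438), or 7.7 to 18.6 months. Every illustrated value lies inside it.

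**The case against.** The strongest case against is that little planned output depends on the definition. The plan promises no PFS median, curve or test. PFS does not appear among the secondary objectives in Section 3.1.2. The one time-to-event comparison it states is with TTP, for which censoring deaths is a usable rule. A sentence that lists the event itself as a censoring date is visibly garbled, so it may be a drafting slip behind which progression or death was meant to be the event. On this view the fault is a wrong name.

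Much of that is fair, and it limits the severity. It does not remove the fault. PFS is the only secondary endpoint named, and its only definition is not PFS. If the wording is a slip, the documents do not show which way to correct it: Section 3.3.2 points to counting deaths, and the TTP comparison in Section 14.0 points to censoring them. The sponsor has to choose, preferably before the data are examined.

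A second objection is that the sample median need not move. This is correct. With 20 first events, no other censoring and deaths placed at random, the median is unchanged when all the deaths fall after the tenth event. The probability is 10/20 = 50% for one death, C(10,2)/C(20,2) = 45/190 = 24% for two, and C(10,4)/C(20,4) = 210/4845 = 4% for four. The bias is therefore zero or upward in any one sample, never downward.

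A third objection is that requiring a last progression-free date goes beyond the defect. It is a separate improvement, but it is the usual companion to a PFS definition. It matters here because survival follow-up can outlast progression follow-up.

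**Conclusion.** The concern holds. Followed as written, Section 14.0 yields TTP with deaths censored under the name PFS, and its censoring sentence cannot be programmed literally. The error in reported PFS is upward or nil.

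Its size depends on the share of first events that are deaths without recorded progression, which the documents do not give. Shares of 5% to 30% inflate the median by 5% to 43% under constant hazards, and at 20% the inflation runs from 16% to 32% across the two Weibull shapes tried. These figures assume that all 20 patients have a first event, whereas accrual is up to 20. They also describe a median that the plan does not commit to report.

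The consequence is confined to a descriptive, unpowered secondary endpoint, and at this sample size the bias lies within sampling error. The primary analysis of change in FES uptake is unaffected. The point should be fixed, but it does not threaten the study's main conclusion.

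**What to change.** Rewrite the last paragraph of Section 14.0 on these lines:

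- **PFS:** time from start of endocrine therapy to the earlier of first recorded progression or death from any cause. Patients with neither are censored at the last date on which they were known to be progression-free.
- **Censoring clause:** remove both progression and death from the PFS censoring dates.
- **Late deaths:** state how a death long after progression follow-up ended is handled, since the new definition would otherwise count it as an event at the date of death.
- **TTP:** if it is kept for the comparison with FES uptake, define it separately and say how deaths without progression are treated.
- **Labels:** use the same name for the same quantity in Section 3.3.2 and throughout Section 14.0, and state in Section 17.0 which one the descriptive analyses use.

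The cost is one paragraph and one data field. Section 8.1 already records the dates of progression and death. The last progression-free date is not listed there and no follow-up disease assessment is scheduled, but it can be taken from clinical records, because Section 6.1 requires that "Patients must agree to allow access to clinical records regarding response to treatment and long term follow up". Sample size, study procedures and the primary analysis do not change.

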15.0 DATA AND SAFETY MONITORING PLAN

Institutional support of trial monitoring will be in accordance with the FHCRC/University of Washington Cancer Consortium Institutional Data and Safety Monitoring Plan. Under the provisions of this plan, FHCRC Clinical Research Support (CRS) coordinates data and compliance monitoring conducted by consultants, contract research organizations, or FHCRC employees unaffiliated with the conduct of the study. Independent monitoring visits occur at specified intervals determined by the assessed risk level of the study and the findings of previous visits per the institutional DSMP.

In addition, protocols are reviewed at least annually and as needed by the Consortium Data and Safety Monitoring Committee (DSMC), FHCRC Scientific Review Committee (SRC) and the FHCRC/University of Washington Cancer Consortium Institutional Review Board (IRB). The review committees evaluate accrual, adverse events, stopping rules, and adherence to the applicable data and safety monitoring plan for studies actively enrolling or treating subjects. The IRB reviews the study progress and safety information to assess continued acceptability of the risk-benefit ratio for human subjects. Approval of committees as applicable is necessary to continue the study.

The trial will comply with the standard guidelines set forth by these regulatory committees and other institutional, state and federal guidelines.

16.0 DATA MANAGEMENT/CONFIDENTIALITY

Source data will include all signs collected during this research. This includes:

- All imaging data, including scan images
- Vitals and physical exams collected at clinic visits
- Labs:
 - Hematology: CBC, differential, platelets
 - Serum Chemistries: including calcium, magnesium, SGOT, SGPT, alkaline phosphatase, LDH, total bilirubin, BUN, creatinine, electrolytes, and glucose

The imaging will be stored on an encrypted hard drive and treated as source. Only the appropriately delegated staff will be given the password to access this data.

The investigator will ensure that data collected conform to all established guidelines. Each subject is assigned a unique subject number to protect subject confidentiality. Subjects will not be referred to by this number, by name, or by any other individual identifier in any publication or external presentation. The licensed medical records department, affiliated with the institution where the subject receives medical care, maintains all original inpatient and outpatient chart documents.

17.0 STATISTICAL CONSIDERATIONS

Analysis Plan

The primary application will be pilot studies with enrollment of about 20 patients, in which the in vivo effects of endocrine-targeted therapy are measured by serial FES PET. The primary endpoints will be quantitative and qualitative measures of FES uptake, and measures of change in FES uptake between pre-therapy and post-therapy scans (Section 6.10.2). Additionally, patients will be followed for disease progression. Associations among FES and FDG PET measures, progression, and biological correlates (Section 6.10.3) may be examined in descriptive analyses.

An expected primary analysis is to examine whether FES uptake changed on average between serial assessments. This may be assessed by a one-sample test of the percent change in FES SUV. For example, a one-sided test at the 0.05 level of significance could evaluate whether the average percent change in FES SUV was greater than 20%, considered a biologically significant change. In serial FES SUV measurements of heavily-pretreated breast cancer patients, change in FES SUV was approximately normally distributed with a standard deviation of about 25 percentage points, for both patients treated with blocking therapy (tamoxifen or fulvestrant) or non-blocking therapy (aromatase inhibitor). Using this standard deviation and n=20 to test whether the average change was greater than 20%, the power would be 0.97 if the true change is 40%, and 0.85 if the true change is 35%. To conclude only that the average percentage change was different from zero (using a two-sided test at the 0.05 level of significance), power would be 0.95 to detect a true average change of 20% (and 0.85 if the true standard deviation were 30 percentage points).

Other analyses for pilot studies could examine what proportion of patients experienced a threshold in percentage change, or surpassed a targeted follow-up FES SUV value. These percentages will be reported using a 90% Wilson score binomial confidence interval. Width of these confidence intervals for pilot studies of n=20, n=25, and n=30 are given in Table 6.3 for a range of observed percentages.

Table 17.1: 90% Wilson score binomial confidence intervals (CIs) by percent observed and sample size.

observed percentage (CI) for n=20	observed percentage (CI) for n=25	observed percentage (CI) for n=30
0.1 (0.03, 0.26)	0.12 (0.05, 0.27)	0.1 (0.04, 0.23)
0.2 (0.09, 0.38)	0.20 (0.10, 0.36)	0.2 (0.11, 0.34)
0.3 (0.16, 0.48)	0.32 (0.19, 0.48)	0.3 (0.18, 0.45)
0.4 (0.24, 0.58)	0.40 (0.26, 0.56)	0.4 (0.27, 0.55)
0.5 (0.33, 0.67)	0.48 (0.33, 0.64)	0.5 (0.36, 0.64)

Breast cancer is a disease of adults with low frequency of incidence in males. We have not excluded males from participation in our studies and will continue this policy but anticipate that none will enroll due to the rarity of presentation.

Table 6.4. Planned Enrollment.

Ethnic Category	Sex/Gender		
	Females	Males	Total

Hispanic or Latino	3	0	3
Not Hispanic or Latino	17	0	17
Ethnic Category Total of All Subjects	20	0	20
Racial Categories			
American Indian/Alaska Native	0	0	0
Asian	3	0	3
Native Hawaiian or Other Pacific Islander	0	0	0
Black or African American	1	0	1
White	16	0	16
Racial Categories: Total of All Subjects	20	0	20

Males will not be excluded; however, breast cancer is rare in males.

Patients will be recruited from participants in other studies requiring [¹⁸F]FES PET. Over the course of this study, more studies will be added requiring [¹⁸F]FES PET, possibly increasing the enrollment target. The IRB will be made aware of changes to enrollment targets.

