3.4 Estimated Accrual

We anticipate that we will enroll up to 20 patients in this pilot study.

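### The four stated powers are known-variance z-test values; a one-sample t-test at n=20 gives 0.96, 0.83, 0.92 and 0.81 instead of 0.97, 0.85, 0.95 and 0.85

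*Combined protocol and SAP*

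**What the plan says.** Section 17.0 (Analysis Plan) describes an expected primary analysis of whether FES uptake changed on average between scans: "This may be assessed by a one-sample test of the percent change in FES SUV". It does not say whether that test is a z-test or a t-test.

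Two versions are given.

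- **Against 20%.** The plan says that "a one-sided test at the 0.05 level of significance could evaluate whether the average percent change in FES SUV was greater than 20" per cent. The planning variability comes from earlier serial FES data, described as "approximately normally distributed with a standard deviation of about 25 percentage points". At n=20, "the power would be 0.97 if the true change is 40%, and 0.85 if the true change is 35" per cent.
- **Against zero.** The aim is to conclude that the mean change is "different from zero (using a two-sided test at the 0.05 level of significance"). Here, "power would be 0.95 to detect a true average change of 20% (and 0.85 if the true standard deviation were 30 percentage points").

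On numbers, section 3.4 says "We anticipate that we will enroll up to 20 patients in this pilot study", and section 17.0 speaks of about 20. The power statement makes no allowance for patients without an evaluable repeat scan.

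**The concern.** With 20 patients and a standard deviation estimated from those same patients, the usual one-sample test is a t-test with 19 degrees of freedom. It has a larger critical value than the normal test and somewhat less power. The stated figures look like normal-theory values, which would be right only if the standard deviation were known in advance.

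These four figures are the only power justification the protocol gives for its expected primary analysis. Section 17.0 also says that the enrolment target may rise as further studies are added. Anyone revisiting the target would start from powers that are too high, and would see more room for lost scans than there is.

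**Working it through.** **Inputs (section 17.0).** n = 20 and level 0.05. Scenarios 1 and 2 are one-sided against 20% with SD 25; scenarios 3 and 4 are two-sided against zero with SD 25 and 30. The distance from the null, δ, is 40 − 20 = 20 in scenario 1, 35 − 20 = 15 in scenario 2, and 20 in scenarios 3 and 4.

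**Step 1: reproduce the stated powers with the SD treated as known.** Power = Φ(δ√n/SD − z), with z = 1.645 one-sided or 1.960 two-sided. The opposite tail is negligible in the two-sided cases.

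1. 20√20/25 = 3.578; Φ(3.578 − 1.645) = 0.973 (stated 0.97)
2. 15√20/25 = 2.683; Φ(2.683 − 1.645) = 0.850 (stated 0.85)
3. 20√20/25 = 3.578; Φ(3.578 − 1.960) = 0.947 (stated 0.95)
4. 20√20/30 = 2.981; Φ(2.981 − 1.960) = 0.847 (stated 0.85)

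All four match to two decimals. Swapping one-sided for two-sided does not reproduce the set under either test (z: 0.947, 0.765, 0.973, 0.909; t: 0.924, 0.721, 0.964, 0.890).

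**Step 2: the same inputs with the SD estimated.** The power is the probability that a noncentral t variable with 19 degrees of freedom and noncentrality δ√20/SD exceeds the t critical value, which is 1.729 one-sided or 2.093 two-sided.

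| Scenario | Stated | z | t, 19 df | Stated minus t, points |
|---|---|---|---|---|
| 1. Against 20%, true 40%, SD 25 | 0.97 | 0.973 | 0.964 | 0.6 |
| 2. Against 20%, true 35%, SD 25 | 0.85 | 0.850 | 0.827 | 2.3 |
| 3. Against 0, true 20%, SD 25 | 0.95 | 0.947 | 0.924 | 2.6 |
| 4. Against 0, true 20%, SD 30 | 0.85 | 0.847 | 0.807 | 4.3 |

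A simulation of the t-test with 400,000 replicates per scenario gave 0.964, 0.827, 0.924 and 0.807.

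**Step 3: can normal critical values be kept?** If the estimated SD is used with 1.645 or 1.960, the true error rate is the tail area of the t distribution with 19 degrees of freedom. That is 0.058 one-sided and 0.065 two-sided, not 0.05. With an estimated SD, the stated level and the stated powers cannot both hold at n=20.

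**Step 4: fewer evaluable pairs.** The documents give no attrition rate, so the numbers of pairs below 20 are assumptions. The t-test powers are:

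| Evaluable pairs | Scenario 1 | Scenario 2 | Scenario 3 | Scenario 4 |
|---|---|---|---|---|
| 20 | 0.964 | 0.827 | 0.924 | 0.807 |
| 19 (assumed) | 0.956 | 0.808 | 0.909 | 0.785 |
| 18 (assumed) | 0.946 | 0.787 | 0.892 | 0.760 |
| 16 (assumed) | 0.920 | 0.740 | 0.848 | 0.703 |

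**Step 5: pairs needed to match.** The smallest numbers of evaluable pairs giving at least the stated powers under the t-test are 21, 22, 23 and 23.

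**The case against.** The strongest reply is that the stated figures contain no slip: they follow exactly from the stated inputs under a normal approximation. The plan never names a t-test, so the shortfall depends on inferring one. The section is worded as illustration, the study is a pilot, and no decision rule or power target turns on 0.85 rather than 0.81. The standard deviation is itself only approximate, and moving it from 25 to 30 costs 10 points on the plan's own figures, more than the change of test does. The lower powers for 16 and 18 pairs come from assumed losses, and section 6.1 admits only patients willing to have serial imaging.

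Much of this stands. The effect is modest, the largest loss falls in the sensitivity case with SD 30, and quoting that case is good practice rather than a sign of doubt about 25. The figures for fewer pairs must be labelled as assumptions and kept apart from the effect of the test itself.

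It does not rescue the stated figures. The plan does not fix the variance for the analysis, and step 3 shows that an estimated SD breaks either the level or the power. Illustrative wording does not make a power correct. Incomplete pairs are also foreseeable: section 11.0 lets patients leave at any time, and sections 4.1 and 11.0 end participation for most adverse events possibly related to the tracer.

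**Conclusion.** The concern holds. The four powers are known-variance values. For the t-test that an estimated standard deviation calls for, they are 0.96, 0.83, 0.92 and 0.81. Three of the four are overstated by more than 2 points, the largest overstatement being 0.85 against 0.81. Scenario 1 is barely affected.

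This rests on percent change being approximately normal, as the plan states, on the standard deviation being estimated from the trial's own data, and on all 20 patients having evaluable paired scans. Under those conditions every power remains above 0.80, so the finding corrects the stated figures and does not challenge the sample size. The margin is thin in the SD-30 case, which falls below 0.80 when one pair is lost.

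**What to change.** In section 17.0, name the one-sample t-test and restate the powers for 20 evaluable pairs as 0.96 and 0.83 (against 20%) and 0.92 and 0.81 (against zero, SD 25 and 30). Say that n means patients with evaluable baseline and repeat FES scans. Add the powers for 18 pairs (0.95, 0.79, 0.89, 0.76) and 16 pairs (0.92, 0.74, 0.85, 0.70), labelled as assumed attrition.

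The cost is a sentence or two in one section and slightly less favourable figures. Enrolment and study procedures do not change.
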